All hospitals within the four health regions of Norway that survey and treat patients with rectal cancer after neo-adjuvant treatment at one of the radiation centres are encouraged to participate and contribute to assessment and inclusion of patients with possible complete or near-complete response. Each cooperating hospital will define a responsible clinician at the respective institution.

Writing group

The writing group will consist of those who created the idea of this national multicentre study ([name], [name], [name]), an oncologist involved in the design of the protocol ([name]) and the primary investigator ([name]). Publication of the core endpoints of the study will be done as a research collaboration that includes all site investigators at university hospitals and collaborating hospitals. The writing group will act as principal author with the responsibility for the process from data analysis to submission of the manuscript. For other manuscripts derived from this study protocol, eligibility for authorship will be considered by the steering group in due time according to the Vancouver criteria for authorship in biomedical publishing. All other participants who do not fulfil criteria for authorship will be acknowledged in all potential publications from this study.

Steering group

The study will be conducted and published on behalf of the Colorectal subgroup of the Norwegian Gastro-Intestinal Cancer Group (NGICG-CR). The steering group of the NGICG-CR will act as steering group for this project.

Abbreviations

CR	Complete response
cCR	Clinical complete response on clinical examination
ypCR	Pathological complete response after neoadjuvant treatment
W&W	Watch and Wait protocol
CRT	Chemoradiotherapy
TME	Total Mesorectal Excision
CRF	Clinical report form
MDT	Multidisciplinary team
LR	Local recurrence
DRE	Digital rectal examination
MRI	Magnetic resonance imaging

Background

During the past three decades, preoperative radiotherapy (RT) and chemoradiotherapy (CRT) was introduced to reduce the high rates, i.e. 25-30%, of local recurrences (LR) after primary resection of adenocarcinoma of the rectum (1-3). For the same reason, a huge effort was done by others to refine the surgical technique of rectal cancer surgery based on better anatomical understanding of the mesorectum and the importance of the mesorectal fascia for optimal surgical treatment – the concept of *total mesorectal excision* (TME) (4).

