In Norway, the implementation of TME as the new gold standard of surgical approach was clearly associated with a significant reduction of LR without the need of neoadjuvant treatment (5). This was, however, not true for very low tumours of the rectum, advanced tumours (i.e., those involving the mesorectal fascia and/or T4 stage), and not for every centre (6). In other countries like Sweden and the Netherlands, preoperative short-course radiotherapy was used in a much larger scale together with the introduction of TME surgery, showing that RT could halve the LR rate (2, 7). The combination of radiation with chemotherapy resulted in downsizing, and thus often down-staging of the tumour (1). Consequently, the use of preoperative CRT has increased in Norway during the years (8). Notably, it appeared that in some of the specimens after resection the tumour had disappeared completely and was not longer detectable by histopathology, indicated as pathological complete response (ypCR) (9).

In the late 1990ies the Brazilian group of Habr-Gama (10) identified the concept of *clinical complete response* (cCR), characterised by four clinical post CRT features: 1. Flattening of the tumour site, 2. No ulceration, 3. Whitening of the tumour and 4. Telangiectasia. These four clinical characteristics indicated a true complete response (CR) following CRT as definitive treatment. In their study, as well as described by others, no surgery was performed and the patient was included in a "watch and wait" (W&W) protocol in order to identify potential regrowth at an early stage. (11-14).

The results from the Habr-Gama group inspired several other centres, such as the Maastricht group in the Netherlands (15) and the Vejle group in Denmark (16) to study the phenomenon of cCR and the non-operative treatment strategy. Moreover, an international collaboration (*International Watch&Wait Database*, <http://www.iwwd.org>) has been established to register and monitor patients with cCR in order to assess the oncological outcomes in large patient groups undergoing this treatment.

Currently, it is agreed that true CR can be achieved after different protocols of chemoradiotherapy. The CR rates in specimens after radical surgery vary with tumour stage, being 30-35% for T1, 15-25% for T2, 12-15% for T3, and <10% for T4 stage. The frequency of complete response after surgery (ypCR) has been reported to be 10% in Norway (17).

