The W&W has gained great interest, as it provides the possibility to cure the patients without the need of major surgery and its consequences on functional outcomes and lifelong morbidity, and thus preventing overtreatment. However, this treatment concept is currently regarded as experimental and has not yet become part of commonly accepted guidelines. There is a need to increase the knowledge on the concept of cCR and CR in a population based patient cohort with a standardized treatment algorithm and follow-up.

Aim of the study

The aim of this study is to estimate the rate of regrowth among patients with locally advanced rectal cancer treated with neoadjuvant treatment with radiotherapy or chemoradiotherapy, where complete clinical response has been obtained, and thus to determine the positive predictive value of cCR in a national cohort.

Objectives and endpoints

Primary endpoint is the *rate of regrowth* among patients with cCR who follow the W&W protocol after preoperative radiotherapy or chemo-radiotherapy, in order to determine the positive predictive value of cCR.

Secondary endpoints are

- The rate of cCR after preoperative CRT
- To calculate the diagnostic accuracy of the clinical diagnosis of complete response
- The rate of metachronous distant metastases in patients following the W&W protocol
- The rate of metachronous metastasis and recurrence rate after ypCR
- Overall and cancer-specific survival of patients with cCR following the W&W protocol compared to patients with ypCR, i.e. patients with complete pathologic response after resection.
- Assess the rate of patients who otherwise would have had an APR
- Patient-reported outcome measures, such as Low anterior resection syndrome (LARS) and quality of life (QoL)
- To calculate the costs of treatment for W&W after cCR as compared to surgical treatment
- To assess the diagnostic accuracy of MRI in the diagnosis of complete response

Design

The current study is designed as an open prospective population-based study. All patients diagnosed and treated with radiotherapy or chemo-radiotherapy for rectal cancer in Norway will be eligible for this study, provided signed informed consent given before inclusion.

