- **Complete clinical response** at 6-8 weeks after neoadjuvant treatment includes two *negative signs*, i.e., the disappearing of the visible tumour leaving a flattening of the mucosa on the inner bowel wall, no tumour is seen, and the disappearing of any ulcer. These signs are *mandatory*. Two other criteria include *positive signs*, i.e., whitening of the previous tumour site appearing almost as a small white spot to merely a great area, and development of telangiectasia. These positive signs depend to a higher degree on time and individual interpretation, and are *not mandatory*:
 1. Flattening of the tumour site (mandatory)
 2. No ulcer visible (mandatory)
 3. Whitening of the tumour site (not mandatory)
 4. Visible telangiectasia (not mandatory)
- **Near Clinical Complete Response (near-cCR)** is defined as a nearly complete disappearance of the tumour and/or the ulcer of more than 75% at 6-8 weeks post RCT as determined by the clinician. A near-cCR may result in cCR after 11-12 weeks post CRT, and in this case the patient will be eligible for inclusion into the W&W

protocol at that time. Otherwise, the condition is not a cCR and surgery is offered immediately.

Patients with cCR after preoperative CRT who decline the W&W protocol and wish to undergo surgery, or patients with near, but not complete clinical response will be asked to give consent to participate for registration in the database as controls.

Exclusion Criteria

- Patients without cCR
- Patients unable to give informed consent
- Patients with short course radiotherapy (5x5 Gy) without additional chemotherapy, or patients receiving less than 40 Gy in long course CRT
- Patients with cCR but with increasing tumour growth on MRI after preoperative treatment
- Patients with metastatic disease at the time of diagnosis with the exception of those who are eligible for "liver first" treatment approach as part of an intention to cure approach.
- Patients previously diagnosed and treated for malignant disease in the pelvic region with radio- or chemoradiotherapy
- Other circumstances that may interfere with successful participation in the W&W protocol

Radiation and chemoradiation

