Neoadjuvant treatment will be given based on a decision by the MDT and according to national guidelines that apply at any given time during the study period. Preoperative radiotherapy is currently given as long course radiotherapy to 50 Gy with concomitant chemotherapy (capecitabine or 5-fluorouracil). Patients treated with short-course 5x5 Gy with combination chemotherapy are also eligible for participation. Neoadjuvant treatment with any modifications due to patient-related factors are acceptable as far as the effect of received treatment is considered to be at least 80% of standard treatment.

Response evaluation before enrolment in the study

All patients who receive preoperative CRT will be evaluated for treatment response at approximately 6 weeks after the last radiation treatment by MRI and clinical examination, including digital rectal examination (DRE) and rigid proctoscopy.

Patients with cCR (i.e., ycT0N0) will be invited for participation in the study.

Patients with near-cCR will be invited to undergo a second evaluation for cCR at 12 weeks for participation in the study. State of clinical tumour regress will be documented by endoscopic photography imaging when cCR is concluded. Patients with initial near-cCR, but without cCR at 12 weeks will be advised to undergo surgery according to current guidelines. The accuracy of DRE in cCR is not evident. When either DRE and/or MRI suggest a tumour in patients who otherwise fulfil cCR criteria, they are offered surgery and asked for inclusion into the study without W&W protocol.

Patients who fulfil the criteria for cCR as defined at 6 weeks or 12 weeks will be asked for participation in the W&W protocol. All other patients who were considered for cCR without a final diagnosis of cCR will not be eligible for the W&W protocol, but they will be asked to participate in the study by recording their data of treatments and outcomes in order to calculate the necessary statistics (e.g., sensitivity, specificity or likelihood ratios of possible prognostic or predictive factors for the study endpoints). These patients will be offered systematic follow-up as described in national guidelines.

Treatment course of the included patients and follow-up

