Estimation of sample size is based on the aim of this study to detect the sensitivity (i.e., true positives) and specificity (i.e., true negatives), as well as 1-sensitivity (false positives) and 1-specificity (i.e., false negatives) in order to characterize the ability to correctly diagnose patients with cCR with a minimum of regrowth (i.e., false negatives) or unnecessary resections (i.e., false positives). Based on these estimations, it will be possible to achieve the primary endpoint of the study, i.e. the rate of regrowth, and to calculate positive predictive value of the diagnosis of cCR among patients who follow the W&W protocol after preoperative chemoradiotherapy.

As the present study is a prospective observational study, and not a clinical trial that aims to prove the superiority or non-inferiority of a specified treatment, power calculations that result in *numbers needed to treat or to harm*, do not apply here for the estimation of number of patients to include.

By including patients into the study who wish to undergo surgical resection despite the clinical finding of cCR, and decide not to follow the W&W algorithm, it will be possible to calculate these parameters based on a 2x2 table on the following assumptions based on results from current literature:

- During this time period, a tenfold/approx. 1000 patients will receive neo-adjuvant treatment
- Of those, 100 patients with cCR to enter the W&W protocol
- Of those 100, it may be assumed that
 - 85 will have a true CR
 - 15 will have ypCR (i.e., ypT0) after surgical resection
 - of those 100 patients, up to 30 may have regrowth after initial cCR within the W&W protocol
- Finally, 900 of 1000 (i.e., 870 patients + 30 patients with regrowth) will have ypT1-4 after surgical resection

Accordingly, the study aims to include at least 100 patients with cCR who choose to follow the W&W algorithm.

	True CR	No CR	
W&W (cCR)	True positive N=85	False positive N=30 (regrowth)	115
No W&W (No cCR)	False Negative N=15	True Negative N=870	885
	100	900	1000

Based on these figures, it will be possible to calculate sensitivity, specificity, 1-sensitivity, 1-specificity, positive and negative predictive values, positive and negative likelihood ratios, and perform ROC curve analysis.

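### Pathological complete response is defined by T category alone (ypT0) while clinical complete response is glossed as ycT0N0, so a resected ypT0N+ patient counts as a complete responder

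*Protocol*

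**What the plan says.** **Pathological side.** In the Protocol, Study population and sample size, the planning assumptions state "15 will have ypCR (i.e., ypT0) after surgical resection". The remaining 900 of 1000 patients, made up of 870 operated patients and 30 with regrowth, "will have ypT1-4 after surgical resection". Neither category mentions nodes.

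The other descriptions of ypCR carry no T or N category:
- Abbreviations: "Pathological complete response after neoadjuvant treatment".
- Background: tumour "not longer detectable by histopathology, indicated as pathological complete response (ypCR").
- Objectives and endpoints, for the survival comparison: "patients with ypCR, i.e. patients with complete pathologic response after resection".

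ypN0 and ypT0N0 appear nowhere.

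**Clinical side.** Response evaluation before enrolment states "Patients with cCR (i.e., ycT0N0) will be invited for participation in the study". This is the only place where N0 is attached to cCR. The itemised criteria under the heading on who is offered the Watch & Wait protocol begin with "Flattening of the tumour site (mandatory") and go on to ulcer, whitening and telangiectasia. All four are luminal. The MRI regression grade and the two confidence scales in Appendix I have no nodal item either.

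**Use of the definitions.** The planning 2x2 table has 85 true positives ("True positive N=85"), 30 false positives labelled as regrowth, 15 false negatives and 870 true negatives. ypCR is also the population for the secondary endpoints on metastasis and recurrence after ypCR, and the comparator for survival of watch-and-wait patients.

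**The concern.** The categories ypT0 and ypT1-4 divide resected patients by T category only. A patient whose primary tumour has gone but whose nodes contain cancer fits the first and cannot fit the second. Such patients are in scope, because the inclusion criteria admit stage I-III disease.

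Two kinds of result are exposed.

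- **Diagnostic accuracy of cCR and MRI (secondary endpoints).** If a ypT0N+ patient was not called cCR, the clinical judgement was right because cancer remained. The T-only rule nevertheless scores it as an error, a false negative in the table's labelling.
- **The ypCR group.** The group used for survival, metastasis and recurrence could contain patients with residual nodal cancer, while the watch-and-wait group is described at entry as node-negative. If node-positive patients fare worse, which is an assumption, the comparison is tilted in favour of watch and wait. The ethics section names possible under-treatment as the harm to be weighed, so the direction of this bias matters.

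**Working it through.** **Inputs from the protocol table:** TP = 85, FP = 30, FN = 15, TN = 870.

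**Input not in the protocol:** q, the share of ypT0 patients with positive nodes. I assume 5% to 15%.

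**Step 1: reproduce the plan's table.**
- Margins: 85 + 30 = 115; 15 + 870 = 885; 85 + 15 = 100; 30 + 870 = 900; total 1000. All agree with the printed margins.
- Sensitivity = TP/(TP + FN) = 85/100 = 85.0%.
- Specificity = TN/(TN + FP) = 870/900 = 96.7%.
- PPV = TP/(TP + FP) = 85/115 = 73.9%.
- NPV = TN/(TN + FN) = 870/885 = 98.3%.

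**Step 2: find which cell depends on the T-only rule.**
- The 85 true positives sit in the watch-and-wait row. They are verified by absence of regrowth, not by a specimen.
- The 30 false positives are regrowths.
- The 15 false negatives are the ypT0 patients. Under a ypT0N0 standard, 15q of them leave the complete-response column and become true negatives.

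**Step 3: recompute with the node-positive patients moved.** Sensitivity = 85/(85 + 15(1 - q)), and NPV = (870 + 15q)/885.

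| q | patients moved (15q) | sensitivity | NPV |
|---|---|---|---|
| 0 (as printed) | 0 | 85/100 = 85.0% | 870/885 = 98.3% |
| 5% | 0.75 | 85/99.25 = 85.6% | 870.75/885 = 98.4% |
| 10% | 1.5 | 85/98.5 = 86.3% | 871.5/885 = 98.5% |
| 15% | 2.25 | 85/97.75 = 87.0% | 872.25/885 = 98.6% |

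Specificity at q = 15% is 872.25/902.25 = 96.7%, unchanged to the rounding shown. PPV stays at 85/115 = 73.9%, because no cell in that row moves.

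**Step 4: set the shift against sampling error.** The 95% half-width for 85 of 100 is 1.96 × √(0.85 × 0.15/100) = 7.0 percentage points. The shift is 0.6 to 2.0 points.

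**Step 5: the comparator.** Under the same assumption, 5-15% of the ypCR group would be node-positive. If their event-free proportion differs from that of ypT0N0 patients by d, the group figure is displaced by q × d, that is 0.05d to 0.15d. The protocol gives no value for d, so this cannot be made more precise.

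**The case against.** **ypT0 is only a planning gloss.** It sits in a list of assumptions, and the endpoint section speaks of complete pathological response, which many would read as including nodes. This stands in part: the endpoint wording does not itself fix a T-only reading. But the gloss is introduced as an equivalence, its complement confirms it, and no other TNM definition exists. It is a stated rule rather than a detail left open for an analysis plan.

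**The two rows of the table use different definitions.** A reader might infer that nodal disease counts as failure under watch and wait but as response after surgery. The text does not support this. The 30 regrowths are placed in the same ypT1-4 category as the 870 operated non-responders. The protocol never says whether nodal tumour counts as regrowth, so the point is open rather than contradictory.

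**The index test is settled as node-negative.** A reader might also infer this. N0 appears once, in a parenthesis, while the itemised criteria and the MRI scales have no nodal item. The clinical definition is itself inconsistent, and correcting only the pathology wording would leave that in place.

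**A different baseline.** Subtracting the 30 regrowths from 100 watch-and-wait patients gives 70 true positives, and so a sensitivity of 70/85 = 82.4%. That is not the printed table, whose true-positive cell is 85. The printed table is the right basis here.

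**The numbers are small and recoverable.** This stands. Pathology reports are collected, so patients can be classified correctly before analysis.

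**Conclusion.** The mismatch is real: read literally, the protocol classes a resected ypT0N+ patient as a complete responder. Its size rests on an assumed node-positive share of 5-15%, for which the protocol gives no figure. On that assumption one or two of the 15 planned false negatives are affected, and sensitivity rises by 0.6 to 2.0 percentage points, well inside sampling error. The ypCR comparator would carry the same 5-15% of node-positive patients.

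A reader might infer that the primary endpoint is compromised. The calculation does not show that. The regrowth rate and PPV are tied to patients who follow watch and wait, PPV stays at 73.9%, and the target of 100 patients stands. Whether nodal tumour counts as regrowth is a separate ambiguity to be closed, not a demonstrated bias. The consequences are limited to the secondary accuracy endpoints and the endpoints built on ypCR.

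**What to change.** 1. Define ypCR once as ypT0N0, with complement ypT1-4 and/or ypN+. Use this definition in the 2x2 table, in the accuracy endpoints and in the secondary endpoints that rely on ypCR.
2. Reconcile the four luminal cCR criteria with the ycT0N0 gloss in the response-evaluation section. Which of the two governs entry is for the sponsor to decide; the passages should agree.
3. State whether nodal or mesorectal tumour counts as regrowth, so that both rows of the table rest on one definition of complete response.

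**Cost.** A few sentences. Pathology reports are already on the data collection list, so no new data item is expected and the sample size is unaffected. The downside is a slightly smaller ypCR comparator group, by 5-15% under the assumption used above.

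### The planning 2x2 table equates treatment chosen with test result, so patients with cCR who choose surgery have no correct cell and sensitivity, specificity, NPV and LR- are distorted

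*Protocol*

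**What the plan says.** All places are in the Protocol.

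- *Study population and sample size* bases the sample size on sensitivity and specificity. It says a 2x2 table can be filled "By including patients into the study who wish to undergo surgical resection despite the clinical finding of cCR".
- The assumptions that follow start from about 1000 treated patients: "Of those, 100 patients with cCR to enter the W&W protocol". Listed under those 100 are "85 will have a true CR", "15 will have ypCR (i.e., ypT0) after surgical resection" and "of those 100 patients, up to 30 may have regrowth after initial cCR within the W&W protocol". The last bullet reads "Finally, 900 of 1000 (i.e., 870 patients + 30 patients with regrowth) will have ypT1-4 after surgical resection".
- The table's first row is W&W, with cCR in brackets: "True positive N=85" and 30 false positives (regrowth), total 115. The second row is no W&W, with no cCR in brackets: 15 false negatives and 870 true negatives, total 885. Column totals are 100 and 900.
- From these figures the section promises sensitivity, specificity, both predictive values, both likelihood ratios and a ROC analysis.
- *Objectives and endpoints* makes the accuracy of the clinical diagnosis of complete response a secondary endpoint.
- The section on who is offered W&W provides for patients with cCR who decline it and have surgery. They are asked to be registered as controls.
- *Response evaluation before enrolment in the study* records patients who were considered for cCR but did not finally receive that diagnosis, so that sensitivity and specificity can be calculated.

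**The concern.** In an accuracy table the rows must be the test result. Here the test is the cCR call at 6 or 12 weeks, and W&W is the treatment that may follow it. The two are not the same, because the Protocol deliberately enrols patients with cCR who go to surgery. Those are the very patients said to make the table calculable, yet the table has no row for them: their test result belongs in the first row and their treatment in the second.

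If the printed labels are followed, the second row takes them in. A decliner with ypT0, whom the test called correctly, becomes a false negative. A decliner with residual tumour, whom the test called wrongly, becomes a true negative. Patient preference would then be reported as diagnostic performance, within a named secondary endpoint.

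**Working it through.** **1. The printed table.** The margins add up: 85 + 30 = 115, 15 + 870 = 885, 85 + 15 = 100, 30 + 870 = 900. The implied measures, which the Protocol does not print, are:

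- sensitivity = TP/(TP + FN) = 85/100 = 85.0%
- specificity = TN/(TN + FP) = 870/900 = 96.7%
- PPV = TP/(TP + FP) = 85/115 = 73.9%
- NPV = TN/(TN + FN) = 870/885 = 98.3%

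**2. How many of the 15 had cCR?** The bullets and the table point different ways. The bullet on the 15 is nested under 100 patients with cCR, and the lead-in speaks of cCR patients who choose resection; on that reading the 15 are test-positive. But 85 + 15 rebuilds the true-CR column total and 870 + 30 the no-CR column total, so the 15 can equally be ypT0 patients never called cCR. Nor are the bullets coherent in themselves: 85 true responders plus up to 30 regrowths make 115, which cannot all come from the same 100. Let k of the 15 be cCR-positive and move them to the cCR row:

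| k | Sensitivity | PPV, all cCR-positive | NPV |
|---|---|---|---|
| 0 | 85/100 = 85% | 85/115 = 73.9% | 870/885 = 98.3% |
| 5 | 90/100 = 90% | 90/120 = 75.0% | 870/880 = 98.9% |
| 10 | 95/100 = 95% | 95/125 = 76.0% | 870/875 = 99.4% |
| 15 | 100/100 = 100% | 100/130 = 76.9% | 870/870 = 100% |

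The PPV column adds no decliners with residual tumour, because the Protocol gives no count for them. Specificity stays at 96.7% for the same reason.

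**3. What the row labels do, whatever k is.** Let s be true sensitivity, p true specificity, d the share of cCR patients with true CR who choose surgery, and e the same share among cCR patients without true CR. Under the printed labels:

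- apparent sensitivity = s x (1 - d)
- apparent specificity = 1 - (1 - p) x (1 - e)

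A perfect test (s = 100%) with d = 15% gives 1.00 x 0.85 = 85%, exactly the table's figure. So the printed 85% cannot be told apart from no diagnostic error at all plus 15% choosing surgery.

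**4. Size if the labels were used in the analysis.** The Protocol gives no share of decliners, so d is assumed here, with d = e. Take the printed cells as the true diagnosis-based cells (TP 85, FP 30, FN 15, TN 870). Apparent TP = 85(1 - d), FN = 15 + 85d, FP = 30(1 - d) and TN = 870 + 30d.

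| d (assumed) | Sensitivity | Specificity | NPV | LR- |
|---|---|---|---|---|
| 0% | 85.0% | 870/900 = 96.7% | 870/885 = 98.3% | 0.150/0.967 = 0.16 |
| 10% | 76.5% | 873/900 = 97.0% | 873/896.5 = 97.4% | 0.235/0.970 = 0.24 |
| 15% | 72.2% | 874.5/900 = 97.2% | 874.5/902.25 = 96.9% | 0.2775/0.972 = 0.29 |
| 30% | 59.5% | 879/900 = 97.7% | 879/919.5 = 95.6% | 0.405/0.977 = 0.41 |

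With d = e the factor (1 - d) cancels from PPV (73.9% throughout) and from LR+ (0.85/0.0333 = 25.5 throughout). Sensitivity and LR- move most.

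**The case against.** **The table is only a planning illustration.** It stands under sample size and rests on assumed figures. The endpoint list and the response-evaluation section both define the test by diagnosis, and a statistical analysis plan that is not shown could define test-positive status properly. It is true that the table need not govern the analysis. But the Protocol itself fixes the labels and cells and promises the accuracy measures from them. The *Statistics* section does not correct them, and the diagnosis-based intent elsewhere contradicts the table.

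**The 15 may be correctly placed.** A reader might infer that all 15 are misclassified true positives and that true sensitivity is 100%. The documents do not establish this. The column totals support the other reading, as does the 10% ypCR frequency that *Background* reports for Norway. The parent bullet speaks of patients who enter W&W, which decliners do not. This part of the objection stands: the number affected is unknown. It does not rescue the labels, since on either reading cCR patients who choose surgery have no correct row.

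**PPV and the primary endpoint.** A reader might also infer that these are biased. The sample-size section ties PPV to patients who follow W&W, and the primary endpoint is regrowth in the same group. Leaving decliners out there is the stated target, not an error.

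**Conclusion.** The table is wrong as written because it equates treatment with test result. That conclusion needs no assumption about the 15: it follows from the row labels and the Protocol's own provision for cCR patients who have surgery.

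The planning sensitivity can be stated only as 85% to 100%, depending on whether 0 or all 15 of the false negatives had cCR. The 100% end should not be taken as an estimate. It means only that, on the bullets, the Protocol supplies no false-negative count at all.

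If the labels were carried into the analysis, sensitivity would fall in proportion to the share of true responders with cCR who choose surgery. For a diagnosis-based value of 85%, it would read 76.5% at an assumed 10% and 59.5% at an assumed 30%. Specificity would be somewhat too high, NPV too low and LR- too large. The NPV direction rests on the equal-declining assumption used in the working.

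The regrowth rate within W&W and the target of 100 W&W patients do not depend on this. The damage is confined to the accuracy endpoint and the planning figures behind it.

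**What to change.** - Define the rows by the cCR call at the 6- or 12-week assessment, whatever treatment followed. cCR-positive is W&W plus cCR with surgery; cCR-negative is all others.
- State the reference: pathology after surgery, regrowth in W&W. Count as false negatives only ypT0 patients without cCR, and count cCR patients with residual tumour at surgery as false positives.
- Restate the planning cells so that bullets and table agree. Say whether the 100 are cCR patients entering W&W or all true responders, how many of the 15 had cCR, and how a W&W row of 115 relates to 100 W&W patients.
- Keep PPV in W&W patients as stated. PPV in all cCR-positive patients is an optional addition.

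The cost is a relabelled table, a sentence on the row rule and a reconciled list of assumptions. No new data are needed, because response assessment and pathology reports are already to be recorded for the surgical controls. No treatment rule changes.
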